Abbreviations used in this table may be found in Appendix 13 .	Day -28 to Day-1	Day 1 (fasted)	Day 4 (fasted)	Day 7 (fasted)	Day 15 (fasted)	Day 28	Day 84 (fasted)	Day 168 (fasted)	Day 252 (fasted)	Day 364 (fasted)		
 Day relative to start of study intervention (Day 1).
Visit Window						±3 d	±5 d	±5 d	±5 d	±3 d		
 See Section 8.4.3 for follow-up AE and SAE assessments.
CDS2 v2.1 self-administered by participant at home	X	→	→	→	→	→	→	→	→	X	X	
 CDS2 v2.1 should be completed for at least a minimum of 7 consecutive days during screening. For re-screening: CDS2 v2.1 only needs to be repeated if >3 months have elapsed from end of last PRO administration.
Incidental gluten exposure check		→	→	→	→	→	→	→	→	X	X	
 Included in the daily eDiary and reviewed at study visits.
PGIS		X			X	X	X	X	X	X	X	
PGIC					X	X	X	X	X	X	X	
PK/ Immunogenicity Assessments												
PK blood sample		X		X							X	
 PK sampling collected pre-dose (at least 5 minutes prior to infusion) and end of infusion (+2) minutes. Additional sampling will be done at 2.5 hours (±5 minutes) and 4 hours (±5 minutes) after infusion start. An ET PK sample is required if ET visits is within 1 week of the last dose.
ADA sample		X		X		X	X	X	X	X	X	
 On dosing days, samples collected pre-dose (at least 5 minutes prior to infusion).
Safety Assessments												
Serious and nonserious AE monitoring	X	→	→	→	→	→	→	→	→	X	X	
 See Section 8.3 for additional information. See Section 8.4 for additional information.

090177e19fcc12ed\Approved\Approved On: 30-Jan-2024 19:45 (GMT)

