2.2.2. KAN-101

KAN-101 is composed of a synthetic liver-targeting CCI [REDACTED] to a synthetic CCI [REDACTED] peptide domain of wheat alpha gliadin (KAN0009) recognized by the HLA-DQ2.5 haplotype. KAN0009 does not bind to the HLA DQ8 molecule. KAN-101 is a liquid formulation drug product administered parenterally via an IV infusion.

KAN-101 harnesses natural tolerogenic pathways in the liver (Thomson & Knolle, 2010) to reprogram pathogenic immune cells to become tolerant toward specific antigens. KAN-101 specifically targets the immune cells that drive CeD and leaves the otherwise healthy components of the immune system intact to perform their natural, protective functions. The proposed mechanism of action of KAN-101 is receptor-mediated internalization of the molecule into liver cells, and the induction of immune tolerance through subsequent KAN0009 gliadin peptide antigen presentation on the major histocompatibility complex (MHC; class I and II). After KAN-101 internalization into liver cells, the KAN0009 peptide is released from the GP portion and processed intracellularly for presentation by MHC and signaling to gliadin-specific T cells for the induction of immune tolerance and subsequent amelioration of gut pathology.

The mechanisms by which KAN-101 induces immunologic tolerance are mediated by:

- Deletion of antigen-specific T cells
- Induction of anergy/clonal exhaustion of antigen-specific T cells
- Induction of regulatory T cells which control the antigen-specific T cell response

For more information on the nonclinical findings, please see the KAN-101 IB.

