5.1. Inclusion Criteria

Participants are eligible to be included in the study only if all of the following criteria apply:

Age and Sex:

1. Participants aged 18 years to 70 inclusive (or the minimum age of consent in accordance with local regulations) at screening.
 - Refer to [Appendix 4](#) for reproductive criteria for male ([Section 10.4.1](#)) and female ([Section 10.4.2](#)) participants.

Disease Characteristics:

2. Previous diagnosis of CeD, based on documentation in the source data:
 - Positive celiac serology (eg, tissue transglutaminase IgA antibody and/or deamidated DGP IgG)

AND

 - Intestinal histology consistent with \geq Marsh Type 2 ([Section 10.11](#)) or with evidence of villous atrophy.
3. Have HLA-DQ2.5 genotype (HLA-DQA1*05 and HLA-DQB1*02 (homozygotes or heterozygotes)).
4. Negative or weak positive for transglutaminase IgA AND negative or weak positive for DGP-IgA/IgG during screening.
 - For tTG, a result of ≤ 10 U/mL will be considered negative or weak positive.
 - For DGP, a result of < 30 U/mL will be considered negative or weak positive.
5. **Part B ONLY (prior to randomization):** Demonstrates a symptomatic response following a 1-day oral GC performed during Run-in, defined as having at least 1 moderate to severe GI symptom (either diarrhea, abdominal pain, bloating, or nausea) the day of the GC.
 - Refer to [Section 8.2.1.1](#) for symptomatic response criteria.

Other Inclusion Criteria:

6. Have followed a gluten-free diet for ≥ 12 months immediately prior to study entry (self-reported).
7. Capable of understanding the ICD, complying with protocol requirements, and has signed the ICD.

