6.3.2. Incidence of Development of ADA During the Study

Participants positive for ADA (screening, confirmatory, specificity and titer) will be summarized by treatment group and timepoint with number and percent for SAS.

6.3.3. Change in Magnitude of IL-2 Response pre- and post-GC in Peripheral Blood from Baseline to GC at Weeks 12, 24, and 36

These endpoints will not be measured/reported due to study termination.

6.3.4. Change in Magnitude of IL-2 Response pre- and post-GC in Peripheral Blood from GC at Day 15 to GC at Weeks 12, 24, and 36

These endpoints will not be measured/reported due to study termination.

6.3.5. Change in circulating levels of various biomarkers from pre-dose to post-dose on Day 1, 4, and 7

These endpoints will not be measured/reported due to study termination.

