
 • To further characterize the PK profile of KAN-101 following multiple doses in participants with CeD. • To evaluate the immunogenicity of KAN-101. • Assess the incidence of CeD symptoms in participants with CeD. • Compare change in biomarker response in participants with CeD and treated with KAN-101 versus PBO. • Assess durability of biomarker (IL-2) response in peripheral blood of participants with CeD and treated with KAN-101 versus PBO. 
Biopsy Substudy:
 
 • To evaluate the impact of KAN-101 on histology from esophagoduodenoscopy (EGD) biopsy in participants with CeD. • Evaluate the potential relationship between histopathological state and response to 1 day GC 	
 • KAN-101 PK parameters, as data permit: AUCinf (dn), AUClast (dn), Cmax(dn), CL, V. • Incidence of development of anti-drug antibodies (ADA) during the study. • Incidence of CeD symptoms as assessed by Patient Reported Outcomes (PROs) including: celiac disease symptom diary (CDSD) v2.1, patient global impression of change (PGIC) and patient global impression of severity (PGIS). • Change in circulating levels of IL-2 from pre-GC to and post-GC at Weeks 12, 24, and 36. • Change in circulating levels of various biomarkers from pre-dose to post-dose on Day 1, 4, and 7 (This analysis will be performed separately, not be included in the CSR). • Change in circulating levels of IL-2 pre- and post-GC in peripheral blood from Day 15 to Weeks 12, 24, and 36. 
Biopsy Substudy:
 
 • Change from baseline in histology (including, but not limited to, Marsh score, villous height crypt depth ratio, IEL counts) at Week 52. • Correlation between histological state, symptomatic response and biomarker responses (IL-2). (This analysis will be performed separately, not be included in the CSR) 	
 • N/A.

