6.3.2. Incidence of Development of ADA During the Study

Participants positive for ADA (screening, confirmatory, specificity and titer) will be summarized by treatment group and timepoint with number and percent for SAS.

6.3.3. Change in circulating levels of IL-2 from pre-GC to and post-GC at Weeks 12, 24, and 36

These endpoints will not be measured/reported due to study termination.

6.3.4. Change in Circulating Levels of IL-2 Response pre- and post-GC in Peripheral Blood from GC at Day 15 to GC at Weeks 12, 24, and 36

These endpoints will not be measured/reported due to study termination.

6.3.5. Change in circulating levels of various biomarkers from pre-dose to post-dose on Day 1, 4, and 7

These endpoints will not be measured/reported due to study termination.

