Appendix 2. Data Derivation Details

Appendix 2.1. Definition and Use of Analysis Windows in Reporting

Analysis windows will be used for PROs and vital signs, and laboratory tests.

If more than one observation from the same participant falls into the same analysis window, the value closest to the targeted day will be used as the observation for that visit. If two observations are equally close to the targeted day, the later will be used. All observations will, however, be included in the listings.

Table 3. Analysis Windows for PGIS and PGIC

Visit Label	Targeted Day	Analysis window for data sets
Baseline (Screening up to first dosing date)	Day 1	Last observation up to and including first dosing date
Day 15	Day 15	Day 8 – Day 21
Week 4	Day 28	Day 22 – Day 56
Week 12	Day 84	Day 57 – Day 126
Week 24	Day 168	Day 127 – Day 210
Week 36	Day 252	Day 211 – Day 308
Week 52	Day 365	Day 309 – end of study

Table 4. Analysis Windows for Vital Signs

Visit Label	Targeted Day	Analysis window for data sets
Baseline (Screening up to first dosing date)	Day 1	Last observation up to and including first dosing date
Day 4	Day 4 pre-dosing	Day 2 - Day 4 pre-dosing
Day 7	Day 7 pre-dosing	Day 5 - Day 7 pre-dosing
Day 15	Day 15 pre-GC	Day 8 - Day 15 pre-GC
Day 28	Day 28 pre-GC	Day 16 – Day 28 pre-GC
Week 12	Day 84 pre-GC	Day 29 – Week 12 pre-GC
Week 24	Day 168 pre-GC	Week 12 GC +1 day – Week 24 pre-GC
Week 36	Day 252 pre-GC	Week 24 GC +1 day – Week 36 pre-GC
Week 52	Day 364	Week 36 GC +1 day – end of study

Table 5. Analysis Windows for Laboratory Tests

Visit Label	Targeted Day	Analysis window for data sets
Baseline (Screening up to first dosing date)	Day 1	Last observation up to and including first dosing date
Day 4	Day 4 pre-dosing	Day 2 - Day 4 pre-dosing

Table 5. Analysis Windows for Laboratory Tests

Visit Label	Targeted Day	Analysis window for data sets
Day 7	Day 7 pre-dosing	Day 5 - Day 7 pre-dosing
Day 15	Day 15 pre-GC	Day 8 - Day 15 pre-GC
Week 12	Day 84 pre-GC	Day 16 – Week 12 pre-GC
Week 24	Day 168 pre-GC	Week 12 GC + 1 day – Week 24 pre-GC
Week 36	Day 252 pre-GC	Week 24 GC + 1 day – Week 36 pre-GC
Week 52	Day 364	Week 36 GC + 1 day – end of study

Table 6. Analysis for Immunogenicity

Visit Label	Targeted Day	Analysis window for data sets
Baseline (Screening up to first dosing)	Day 1 pre-dosing	Last observation prior to first dosing date
Day 7	Day 7 pre-dosing	Day 2 - Day 7 pre-dosing
Week 4	Day 28	Day 8 – Day 56
Week 12	Day 84	Day 57 – Day 126

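### The Part B and Part C SAPs name incidence of ADA development as an endpoint but plan only per-visit positivity, and the Part C ADA baseline window contradicts its own row

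*SAP*

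**What the plan says.** Section 2.2 (Table 2) of the Part B and Part C SAPs gives the endpoint as "Incidence of development of anti-drug antibodies (ADA) during the study". Section 6.3.2 of both gives the whole analysis: "Participants positive for ADA (screening, confirmatory, specificity and titer) will be summarized by treatment group and timepoint with number and percent for SAS". Protocol 9.3.7 adds only that immunogenicity is summarized descriptively. After termination, ADA is the one exploratory endpoint still reported in Part B. In Part C it is kept together with descriptive patient-reported outcomes up to Week 12.

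SAP Section 3.3 (both parts) places ADA assessments on Days 1, 7 and 28 and at Weeks 12, 24, 36 and 52, or at early termination. There is no screening sample. The Part C Schedule of Activities (protocol 1.3.3) has samples on dosing days drawn before the infusion, and it counts days from the start of study intervention, so Day 1 is the first dosing date.

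The baseline row of Table 6 in the Part C SAP, Appendix 2.1, has three cells. The label runs from screening to first dosing, the targeted day is Day 1 before dosing, and the window is "Last observation prior to first dosing date". The next window opens on Day 2. Tables 3 to 5 of the same appendix let the baseline include the first dosing date.

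**The concern.** Development of ADA is a change within a participant, from no antibody before treatment to antibody afterwards. A table of positives at each visit does not show whether the positives at Day 28 and Week 12 are the same people, or whether any were already positive on Day 1. Neither the protocol nor the SAPs define developed or treatment-emergent ADA, an ever-positive count, a denominator of participants with evaluable samples, or a rule for participants positive at baseline.

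Pre-existing reactivity cannot be dismissed here. Protocol 2.2.2 describes KAN-101 as carrying a "peptide domain of wheat alpha gliadin (KAN0009) recognized by the HLA-DQ2.5 haplotype". Inclusion criterion 4 admits participants who are "negative or weak positive for DGP-IgA/IgG during screening". Without a baseline rule, antibody present before treatment and antibody that follows treatment enter the same count.

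The Table 6 wording adds a practical risk in Part C. A programmer who codes the window cell alone will produce no baseline category, and the Day 1 result will drop out of the by-timepoint table.

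**Working it through.** The documents give no ADA rate, sample size or power, so there is no planned figure to reproduce. Two checks apply.

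**1. Scheduled Part C samples against the Table 6 windows, read literally**

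| Scheduled sample | Window that contains it |
|---|---|
| Day 1 pre-dose | none (baseline ends before the dosing date; next window starts Day 2) |
| Day 7 pre-dose | Day 7 (Day 2 to Day 7 pre-dose) |
| Day 28 | Week 4 (Day 8 to 56) |
| Day 84 | Week 12 (Day 57 to 126) |
| Day 168 | Week 24 (Day 127 to 210) |
| Day 252 | Week 36 (Day 211 to 308) |
| Day 364 | Week 52 (Day 309 to end of study) |

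Six of the seven samples fall in exactly one window and Day 1 falls in none. If the baseline window takes in the Day 1 pre-dose sample, as the row's target and label imply, all seven fall in exactly one.

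**2. What per-visit counts say about incidence**

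If *k* of *n* participants are positive at each of *T* visits after the first dose, the number ever positive lies between *k* (the same people each time) and min(*n*, *k* × *T*) (different people each time).

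Inputs: *n* = 26 per group in Part C and 4 per group in Part B (protocol 9.5 and 4.1.2). *T* = 6 for the full schedule (Day 7, Day 28, Weeks 12, 24, 36, 52) and *T* = 3 up to Week 12. The values of *k* are assumed.

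- Part C, *k* = 3, *T* = 3: 3 to min(26, 9) = 9, that is 3/26 = 11.5% to 9/26 = 34.6%.
- Part C, *k* = 3, *T* = 6: 3 to min(26, 18) = 18, that is 11.5% to 18/26 = 69.2%.
- Part B, *k* = 1, *T* = 3: 1 to min(4, 3) = 3, that is 1/4 = 25% to 3/4 = 75%.
- Part B, *k* = 1, *T* = 6: 1 to min(4, 6) = 4, that is 25% to 4/4 = 100%.

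Now suppose that the same 3 of 26 are positive at every later visit, and that *b* of them were already positive on Day 1. New onset among those negative at baseline is (3 − *b*)/(26 − *b*):

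- *b* = 0: 3/26 = 11.5%.
- *b* = 1: 2/25 = 8.0%.
- *b* = 3: 0/23 = 0%.

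The post-dose columns of the planned table are identical in all three cases.

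**The case against.** The best defence is that the information is there. The Table 6 row names Day 1 before dosing as its target, SAP 3.3 lists Day 1 as an ADA day, and Appendix 2.1 keeps every observation in the listings. On that reading the by-timepoint table shows Day 1 positivity by group, and a reader can allow for it. For example, if 20% are positive on Day 1, all of them stay positive, and 28% are positive later, then new onset is (0.28 − 0.20)/(1 − 0.20) = 10%. Placebo shows the same background. The endpoint is also exploratory, and protocol 9.3.4 says such results serve internal purposes and may not appear in the study report.

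Much of this stands. A reader might infer from the window cell that no participant would have an ADA baseline, or that the endpoint is out of reach. The documents do not support that: the row contradicts itself rather than plainly excluding Day 1, and incidence can be derived from samples already scheduled. The subtraction, however, works only if baseline positives stay positive and later positives are the same people from visit to visit. The table cannot show either.

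Three further inferences also lack support:

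- **That pre-existing ADA is common.** No pre-dose ADA rate is given, nor any evidence that celiac serology cross-reacts in the ADA assay.
- **That ADA bears on the closure of Part B.** Protocol 4.2 attributes the closure to possible sensitization by the screening gluten challenge and to adverse events, and does not mention ADA.
- **That the Day 15 challenge distorts the Day 28 sample.** All Part C groups have the same challenge at the same time, and nothing shows that it changes ADA.

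**Conclusion.** The point holds as a gap in specification. In both parts the planned summary gives prevalence by visit and not the named endpoint, however Table 6 is read. In Part C the baseline row also contradicts itself and must be reconciled. The window finding is limited to Part C, because the Part B immunogenicity table cannot be read in the available text.

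Its size depends on the data. The ranges above rest on assumed positivity and show only how loosely per-visit counts bound incidence: 11.5% to 69.2% in a Part C group with 3 positives at each of six visits. If ADA is rare, or the same participants are positive throughout and none was positive on Day 1, the practical effect is small. The endpoint is exploratory and descriptive, so no power, alpha or primary conclusion is affected. It should still be corrected, because it remains among the few exploratory results to be reported.

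**What to change.** - **Part C SAP, Appendix 2.1, Table 6.** Set the baseline window to the last observation up to and including the Day 1 pre-dose sample. Check that the Part B immunogenicity table agrees.
- **Part B and Part C SAPs, Section 6.3.2.** Add one per-participant row per group for treatment-emergent ADA: negative at baseline and positive at any visit after the first dose. If wanted, add a second component for participants positive at baseline whose titer rises by a pre-set amount. The documents give no threshold, so the sponsor should fix it before looking at ADA results by group.
- **Denominator.** Use participants with a baseline sample and at least one sample after the first dose.
- **Presentation.** Show baseline positivity separately, put placebo alongside the dose groups descriptively, and keep the by-timepoint table as support.

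The cost is one table cell, a few lines of SAP text and one derived variable. The samples and titers are already planned, so no new blood draw is needed.

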Appendix 2.2. Celiac Disease Symptom Diary (CDS)

COPYRIGHTED MATERIAL

[Redacted content]

090177e1a3cca9df\Approved\Approved On: 06-Aug-2025 19:40 (GMT)

COPYRIGHTED MATERIAL
[Redacted]

[Redacted]

[Redacted]

[Redacted]

[Redacted]

[Redacted]

Appendix 2.3. Patient Global Impression of Severity (PGIS)

COPYRIGHTED MATERIAL
[Redacted]

- [Redacted]
- [Redacted]
- [Redacted]
- [Redacted]
- [Redacted]

Appendix 2.4. Patient Global Impression of Change (PGIC)

COPYRIGHTED MATERIAL
[Redacted]

- [Redacted]
- [Redacted]
- [Redacted]
- [Redacted]
- [Redacted]

Appendix 3. List of Abbreviations

Abbreviation	Term
ADA	anti-drug antibodies
ADL	activity/activities of daily living
AE	adverse event
AKI	acute kidney injury
ALP	alkaline phosphatase
ALT	alanine aminotransferase
ANC	absolute neutrophil count
ANCOVA	analysis of covariance
ANOVA	Analysis of variance
AST	aspartate aminotransferase
AUC	area under the curve
AUC _{inf} (dn)	dose normalized AUC _{inf}
AUC _{inf}	area under the plasma-concentration curve from time 0 extrapolated to infinite time
AUC _{last}	area under the plasma concentration-time profile from time 0 to the time of the last quantifiable concentration (C _{last})
AUC _{last} (dn)	dose normalized AUC _{last}
BP	blood pressure
CDS	celiac disease symptom diary
CeD	celiac disease
CL	apparent systemic clearance
C _{max}	maximum observed concentration
C _{max} (dn)	dose normalized C _{max}
CTCAE	common terminology criteria for adverse events
CV	coefficient of variation
DSMB	data safety monitoring board
ET	early termination
FAS	full analysis set
GC	gluten challenge
GFD	gluten-free diet
GI	Gastrointestinal
GM	geometric mean
GMR	geometric mean ratio
ICD	informed consent document
IL-2	interleukin-2
IRR	infusion-related reactions
LLOQ	Lower Limit of Quantification
min	minimum
max	maximum
N/A	not applicable
PBO	placebo

Abbreviation	Term
PGIC	Patient Global Impression of Change
PGIS	Patient Global Impression of Severity
PK	pharmacokinetic(s)
PKAS	PK analysis set
PRO	patient-reported outcome
PT	preferred term
SAE	serious adverse event
SAP	statistical analysis plan
SAS	safety analysis set
SD	standard deviation
SOC	system organ class
$t_{1/2}$	terminal phase half-life
TEAE	treatment-emergent adverse event
T_{max}	time to reach C_{max}
ULN	upper limit of normal
V	apparent volume of distribution
